# 4.5 Duration of Therapy

In the absence of treatment delays due to adverse events, treatment may continue for one year or until

- Disease progression
- Inter-current illness that prevents further administration of treatment
- Unacceptable adverse event(s)
- Subject decides to withdraw from the study, OR
- General or specific changes in the patient's condition render the subject unacceptable for further treatment in the judgment of the investigator".

## 4.6 Duration of Follow Up

Subjects will be followed every 3 months until 2 years post concurrent durvalumab/RT then every 6mos during year 3-5, then yearly or until death, whichever occurs first.

Subjects who discontinue for reasons other than progressive disease will have post-treatment follow-up for disease status until disease progression, initiating a non-study cancer treatment, withdrawing consent or becoming lost to follow-up. After documented disease progression each subject will be followed for overall survival until death, withdrawal of consent, or the end of the study (whichever occurs first). Subjects removed from treatment for unacceptable adverse events will be followed until resolution or stabilization of the adverse event.

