### 2.4 Endpoints

- 2.4.1 Primary endpoint of 12-month progression-free survival (PFS) rate is based on an assessment by an investigators according to RECIST 1.1 criteria; PFS is defined as the time from the study enrollment to documented progressive disease or death due to any cause, whichever occurs first;
- 2.4.2 Secondary endpoint of safety and tolerability will be assessed by adverse event according to CTCAE V.5;
- 2.4.3 Secondary endpoint of overall survival is defined as the time from study enrollment to death due to any cause;
- 2.4.4 Secondary endpoint of distant metastases free survival is defined as the time from the study enrollment to any new distant lesion;
- 2.4.5 Secondary endpoint of local and regional control defined as the time from the study enrollment to any local and regional lesion;
- 2.4.6 Exploratory endpoint of biomarker and biomarker correlatives;
- 2.4.7 Exploratory endpoint of proportion of patients alive at 12 and 24 months.

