#### 10.2 Accrual

In the PACIFIC trial, patients who received consolidative durvalumab after chemoradiation had a 12-month PFS rate of 55%. PFS was measured starting after completion of chemoradiation, when anti-PDL1 treatment was started. This represents the assumed performance of the experimental arm in this study. We recognize that all patients who were randomized in the PACIFIC trial had tolerated and not progressed on chemoradiation, which represents some degree of selection bias. The possibility of early progression or treatment intolerance were taken into account when selecting the margins for the non-inferiority design of this study. A sample size of 47 achieves 80% power to detect a non-inferiority against an upper hazard ratio of 1.4 using a log-rank test at a 0.1 significance level when the actual hazard ratio is 1.0 and the standard of care group hazard rate is 0.5978 (which is equal to 1-year PFS rate of 55% using an exponential model). Three additional patients will be enrolled (total N=50) to account for 5% loss to follow-up. Patients will be accrued for a period of 3 years with 1-year follow-up.

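### Section 4.6 stops disease follow-up at the start of non-study cancer therapy, which conflicts with the PFS definition and scan schedule and leaves 12-month PFS open to informative censoring

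*Combined protocol and SAP*

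**What the plan says.** Section 2.4 (repeated in 10.1.2) defines the primary endpoint: "PFS is defined as the time from the study enrollment to documented progressive disease or death due to any cause, whichever occurs first". Starting another cancer treatment is neither an event nor an exception. Section 6.1.6 restates PFS with progression only and does not mention new therapy either.

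Section 4.6 contains three rules:

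- Its first sentence follows subjects on a fixed visit schedule until death.
- Subjects who discontinue for a reason other than progression have "post-treatment follow-up for disease status until disease progression, initiating a non-study cancer treatment, withdrawing consent or becoming lost to follow-up".
- Survival follow-up is attached to progression: "After documented disease progression each subject will be followed for overall survival until death".

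The follow-up visits in section 5.3 and the CT footnotes in section 5.4 continue 3-monthly imaging for 2 years, with no stop at new therapy.

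Section 10.2 sizes the trial: "A sample size of 47 achieves 80% power to detect a non-inferiority". The margin is a hazard ratio of 1.4, and the comparison is planned "using a log-rank test at a 0.1 significance level". The assumed true hazard ratio is 1.0, and the reference hazard is 0.5978 per year, that is, 55% PFS at 12 months. Section 10.3.1 names Kaplan-Meier with Greenwood's formula. It gives no censoring rule for new therapy and no sensitivity analysis.

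**The concern.** A progression seen after a switch to non-study therapy is a PFS event under section 2.4, but the second rule in section 4.6 stops looking for it. Under Kaplan-Meier the natural consequence is to censor such a patient at or near the switch. That is harmless only if the patient's later risk matches that of patients still followed.

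There is reason to doubt that here. Section 4.5 lists a change in the patient's condition, as judged by the investigator, as a stopping reason separate from progression. Section 4.4.12 expects radiation change in the lung, usually within the first 6 months, and the CT footnotes allow for progression that is clinically uncertain. Deterioration may therefore come before progression that can be documented. The regimen omits chemotherapy, so chemotherapy is an obvious off-study choice. Treatment stops without progression are not rare either: section 7.1.3 gives 15% discontinuation for adverse reactions in PACIFIC's durvalumab arm. That is not a switching rate, but it indicates the size of the pool.

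The trial is open-label and single-arm, with investigator-assessed progression and no concurrent control subject to the same rule. The margin is narrow in patients: 55% − 43.3% = 11.7 points, about 6 of 50 (0.117 × 50 = 5.85). Post-switch assessments that are not collected cannot be reliably recovered later.

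**Working it through.** **The plan's own figure.** Inputs from section 10.2: reference hazard λ = −ln 0.55 = 0.5978 per year, margin 1.4, alpha 0.10, power 80%, 3 years' accrual plus 1 year of follow-up.

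- Margin hazard: 1.4 × 0.5978 = 0.837 per year, so 12-month PFS at the margin is exp(−0.837) = 43.3%.
- One-sample log-rank, one-sided 0.10. Expected events under the null = (1.2816 + 0.8416 × √(1/1.4))² / (1 − 1/1.4)² = 48.65. Observed events under the alternative = 48.65/1.4 = 34.75.
- Event probability under the alternative = 1 − (e^(−0.5978) − e^(−4×0.5978)) / (3 × 0.5978) = 0.744.
- N = 34.75/0.744 = 46.7, so 47. With 5% loss, 47/0.95 = 49.5, so 50.

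The stated 47 and 50 reproduce with a one-sided test. Section 10.2 does not state sidedness; two-sided one-sample variants need 65 to 75.

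**Effect of the stop.** The documents give neither the switching frequency nor the hazard after a switch. Both are assumptions:

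- f = share who would switch before progression or death over complete follow-up, 5% to 20%.
- k = hazard after the switch divided by hazard before it, 0.5 to 5.

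Pre-switch hazard is b and switching hazard is g = b·f/(1−f). For each f and k, b is set so that true 12-month PFS in the whole cohort equals the margin:

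S(1) = e^(−(b+g)) + g·e^(−kb)·[1 − e^(−(b+g−kb))]/(b+g−kb) = 0.433.

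Example with f = 10%, k = 2: b = 0.809, g = 0.090, and S(1) = 0.407 + 0.026 = 0.433. Censoring at the switch makes Kaplan-Meier estimate e^(−b) = e^(−0.809) = 44.5% instead of 43.3%.

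Trials of N = 50 were then simulated (20,000 per setting; Kaplan-Meier means from 3,000). Non-inferiority was declared when (E − d)/√((E + d)/2) > 1.2816, where d is observed events and E is 0.837 × total person-years. Each cell shows continued follow-up → censoring at the switch.

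| f | k | Switched within 12 months | Mean 12-month KM | False non-inferiority rate |
|---|---|---|---|---|
| 5% | 2 | 2.9% | 43.2% → 43.8% | 0.09 → 0.12 |
| 5% | 3 | 2.9% | 43.1% → 44.1% | 0.09 → 0.13 |
| 10% | 2 | 5.9% | 43.2% → 44.4% | 0.08 → 0.14 |
| 10% | 3 | 5.9% | 43.5% → 45.3% | 0.08 → 0.17 |
| 20% | 2 | 12.4% | 43.2% → 45.8% | 0.07 → 0.20 |
| 20% | 3 | 12.2% | 43.3% → 47.3% | 0.07 → 0.27 |
| 20% | 5 | 11.9% | 43.1% → 48.6% | 0.08 → 0.36 |
| 10% | 1 | 6.0% | 43.2% → 43.1% | 0.10 → 0.10 |
| 10% | 0.5 | 6.1% | 43.1% → 42.0% | 0.14 → 0.07 |
| 20% | 0.5 | 13.4% | 43.4% → 41.2% | 0.18 → 0.05 |

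The continued-follow-up rate departs from 0.10 when k is not 1. The test uses all follow-up while only the 12-month value is fixed at the margin, and survival is then no longer exponential.

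**The case against.** A reader might infer that the plan censors these patients and so tilts the primary result towards non-inferiority. The documents do not support that, for four reasons, all of which stand.

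- **No section states the censoring.** The first sentence of 4.6, section 5.3 and the CT footnotes all point to continued follow-up. What is shown is an unreconciled conflict, not a biased analysis.
- **The direction is open.** The affected patients include those who stop for adverse events or intercurrent illness, and a toxicity stop does not imply a higher progression hazard. At k = 1 there is no bias; at k = 0.5 it reverses.
- **The benchmark is unknown on this point.** The documents do not say how PACIFIC handled new therapy in its 55%. If it censored there too, counting later events only in this trial would create a mismatch.
- **The error rates belong to a test matched to the sizing statement.** Section 10.3.1 plans estimation and does not restate a non-inferiority test.

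A reader might also infer that patients who switch without progression are lost for survival. That goes too far. The opening of 4.6 follows subjects until death, 4.7 keeps subjects removed from therapy in follow-up, 5.5.1 permits follow-up after withdrawal from treatment, and 5.5.9 requires two years of documented contact attempts before a subject may be considered lost. The progression-linked sentence fails to name switchers; it does not exclude them.

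Finally, which handling of new therapy is primary is partly an estimand choice. Counting all later outcomes credits the chemotherapy-free regimen with any benefit of off-study treatment. That is fair, and it is why sensitivity analyses are needed in both directions. None of this removes the conflict in the text.

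**Conclusion.** The conflict is real and should be resolved. Followed as written, the stop discards observations that the primary endpoint definition requires and leaves 12-month PFS open to informative censoring. If 5–20% of patients switch before progression and their hazard is then 2–3 times higher, the nominal 0.10 false non-inferiority rate becomes about 0.12–0.27 (0.07–0.09 with continued follow-up), and mean 12-month Kaplan-Meier reads about 44–47% when the truth is 43.3%.

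These sizes rest on assumed inputs and on the one-sample log-rank test that reproduces N = 47. An optimistic bias is plausible where switching follows clinical worsening, but it is not established, and the net bias against 55% cannot be signed. The sample size is unaffected.

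**What to change.** - In section 4.6, remove the start of a non-study cancer treatment from the list that ends disease-status follow-up, so that the scans already scheduled in section 5.4 continue to progression or death.
- In the same section, state that survival follow-up applies to all enrolled subjects, not only to those with documented progression.
- In section 10.3.1, pre-specify a primary PFS analysis that follows section 2.4: progression or death counts regardless of new therapy.
- Add two sensitivity analyses: (a) censoring at new therapy and (b) counting new therapy as an event. Record the date and type of new therapy so that both can be run.

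The cost is mainly protocol and analysis wording, because the visits and scans are already scheduled; N does not change. The downside is that some post-switch outcomes will reflect the non-study therapy, which may itself favour the regimen. Analysis (b) shows how far the conclusion depends on that.

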# 5.3 Follow-up Procedures

- Follow up visit every 3 months for 2 years; every 6 months for years 3-5; then yearly Procedure
- Physical exam including vital signs
- Performance status
- Adverse event assessment
- Complete blood count and serum chemistries
- Adrenal function tests and thyroid function tests
- Chest CT include adrenals

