#### **ASSESSMENTS IN FOLLOW UP**

Assessments	Every 3 mos until 2 years post concurrent durvalumab/RT then every 6mos during year 3-5, then yearly
History and physical exam	Х
Zubrod performance status	Х
Tumor Measurement	Х
Med Onc exam	Х
AE Evaluation	Х
CBC, BMP	X
CT Chest with contrast and include adrenals	X 

¹After completion of concurrent durvalumab/radiotherapy, radiographic assessment with CT chest with contrast including adrenals will occur within 2 weeks. Further radiographic assessment will occur every 3 months for 2 years. After 2 years, radiographic disease assessment should be performed every 6 months during year 3-5 then annually thereafter. FDG-PET/CT should be done to confirm clinically uncertain progression or treatment related effects at the discretion of the treating investigator. This imaging may be done locally.

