#### 5.5 Removal of Subjects from Study

Subjects can be taken off the study treatment and/or study at any time at their own request, or they may be withdrawn at the discretion of the investigator for safety, behavioral or administrative reasons. The reason(s) for discontinuation will be documented and may include:

- 5.5.1 Subject voluntarily withdraws from treatment (follow-up permitted);
- 5.5.2 Subject withdraws consent (termination of treatment and follow-up);
- 5.5.3 Subject is unable to comply with protocol requirements;
- 5.5.4 Subject demonstrates disease progression (unless continued treatment with study drug/treatment is deemed appropriate at the discretion of the investigator);
- 5.5.5 Subject experiences toxicity that makes continuation in the protocol unsafe;
- 5.5.6 Treating physician judges continuation on the study would not be in the subject's best interest;
- 5.5.7 Subject becomes pregnant (pregnancy to be reported along same timelines as a serious adverse event):
- 5.5.8 Development of second malignancy (except for basal cell carcinoma or squamous cell carcinoma of the skin) that requires treatment, which would interfere with this study;
- 5.5.9 Lost to follow-up. If a research subject cannot be located to document survival after a period of 2 years, the subject may be considered "lost to follow-up." All attempts to contact the subject during the two years must be documented and approved by the Data Monitoring Committee.

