#### 10.0 STATISTICAL CONSIDERATIONS

#### 10.1 Study Design/Study Endpoints

- 10.1.1 Study design: The study is a single armed, phase II trial to evaluate concurrent Durvalumab and radiotherapy followed by consolidative Durvalumab for Stage III Non-Small Cell Lung Cancer (NSCLC).
- 10.1.2 Primary endpoint of 12-month progression-free survival (PFS) rate is based on an assessment by an investigators according to RECIST 1.1 criteria; PFS is defined as the time from the study enrollment to documented progressive disease or death due to any cause, whichever occurs first;
- 10.1.3 Secondary endpoint of safety and tolerability will be assessed by adverse event according to CTCAE V.5;
- 10.1.4 Secondary endpoint of overall survival is defined as the time from study enrollment to death due to any cause;
- 10.1.5 Secondary endpoint of distant metastases free survival is defined as the time from the study enrollment to any new distant lesion:

- 10.1.6 Secondary endpoint of local and regional control defined as the time from the study enrollment to any local and regional lesion:
- 10.1.7 Exploratory endpoint of biomarker and biomarker correlatives;
- 10.1.8 Exploratory endpoint of proportion of patients alive at 12 and 24 months.

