#### 10.3 Data Analyses

#### 10.3.1 Survival outcome

Progression-free survival and overall survival will be estimated using the Kaplan-Meier approach and the corresponding confidence intervals will be estimated using Greenwood's formula. Distant metastases-free survival, local and regional control will be estimated using the Kaplan-Meier approach.

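### Section 4.6 conflicts with 5.3 and 5.4 on whether a second-site failure is recorded after first progression, although both site-specific secondary endpoints need it

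*Combined protocol and SAP*

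**What the plan says.** **Endpoints (2.2, 2.4, 10.1).** "Secondary endpoint of distant metastases free survival is defined as the time from the study enrollment to any new distant lesion". Local and regional control is defined in the same way, as time to any local and regional lesion. Neither definition refers to first failure, and neither names death as an event.

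**Follow-up after progression (4.6).** The one sentence specific to progression reads: "After documented disease progression each subject will be followed for overall survival until death, withdrawal of consent, or the end of the study". Just before it, subjects who stop treatment without having progressed "will have post-treatment follow-up for disease status until disease progression, initiating a non-study cancer treatment, withdrawing consent or becoming lost to follow-up".

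**General schedule.** The opening sentence of 4.6 reads: "Subjects will be followed every 3 months until 2 years post concurrent durvalumab/RT then every 6mos during year 3-5, then yearly or until death". Section 5.3 has the same calendar ("Follow up visit every 3 months for 2 years; every 6 months for years 3-5; then yearly") and lists chest CT. The follow-up table in 5.4 adds tumour measurement, and its footnote says "Further radiographic assessment will occur every 3 months for 2 years". None of these stops at progression. Section 4.7 has subjects taken off therapy followed per protocol, and 5.5 makes progression a reason for removal "unless continued treatment with study drug/treatment is deemed appropriate at the discretion of the investigator".

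**Analysis (10.3.1).** "Distant metastases-free survival, local and regional control will be estimated using the Kaplan-Meier approach". No rule is given for progression at the other site, new anticancer therapy or death.

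**The concern.** An endpoint that counts any distant lesion needs the site of failure to be tracked beyond a first local/regional progression, and the reverse holds for local/regional control. Take a patient whose primary regrows at month 5 and who has a distant lesion at month 8. A site that follows the progression sentence of 4.6 has no instruction to record the second event. A site that follows 5.4 would scan and could record it. Ascertainment may then vary with which section a coordinator reads.

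If the later lesion is not recorded, Kaplan-Meier has little choice but to censor that patient for distant failure at month 5. This is harmless only if patients who have just failed at one site have the same risk at the other site as those still progression-free. If their risk is higher, both curves are too optimistic.

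The direction matters here. The trial removes chemotherapy and asks whether outcomes remain comparable (1.4), and 1.1 quotes the reference trial's time to death or distant metastasis. Distant control is a natural question for this regimen, and an upward bias would flatter it.

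**Working it through.** **The plan's own figure.** The documents give no figure for either site endpoint. The only design figure is N in 10.2, and it reproduces. The hazard is 0.5978 per year, since e^(−0.5978) = 0.550. With 3 years' uniform accrual and 1 year's follow-up, the event probability is p = 1 − (e^(−0.5978) − e^(−4×0.5978))/(3×0.5978) = 0.744. A one-sample log-rank test at one-sided 0.1 with 80% power and margin 1.4 gives n = (1.2816×√1.4 + 0.8416)² / (0.4²×0.744) = 46.7, so 47; 47/0.95 = 49.5, so 50. PFS ends at first progression, so nothing below changes this.

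**Inputs for the illustration.**
- From 10.2: total first-failure hazard 0.5978 per year.
- Assumed: shares of first failure (local/distant/death) of 40/40/20 or 30/50/20.
- Assumed: death hazard after progression μ = 0.8 per year.
- Assumed: after failure at one site, the hazard at the other is multiplied by k.

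**Formulas.** Let h be the hazard for the site of interest (0.5978 × its share), g the hazard for the other site, and c = k·h + μ.
- Censoring at first progression: Kaplan-Meier estimates e^(−h·t).
- Full collection, censoring at death: at time s the patients at risk are those progression-free, P0 = e^(−0.5978s), and those failed only at the other site, P1 = g·(e^(−0.5978s) − e^(−c·s))/(c − 0.5978). The hazard is r(s) = h·(P0 + k·P1)/(P0 + P1), and Kaplan-Meier estimates exp(−∫r) from 0 to t.

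At k = 1, r(s) = h and the two agree exactly.

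**Results** (% free of the event; differences in points, from unrounded values):

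| Shares, endpoint | k | 12 mo: stop / full | Diff. | 24 mo: stop / full | Diff. |
|---|---|---|---|---|---|
| 40/40/20, either | 2 | 78.7 / 77.1 | 1.6 | 62.0 / 58.1 | 3.8 |
| 40/40/20, either | 3 | 78.7 / 75.7 | 3.0 | 62.0 / 55.2 | 6.8 |
| 30/50/20, distant | 2 | 74.2 / 72.8 | 1.4 | 55.0 / 51.8 | 3.2 |
| 30/50/20, distant | 3 | 74.2 / 71.6 | 2.6 | 55.0 / 49.5 | 5.5 |
| 30/50/20, local/regional | 2 | 83.6 / 82.0 | 1.6 | 69.9 / 65.7 | 4.1 |
| 30/50/20, local/regional | 3 | 83.6 / 80.5 | 3.0 | 69.9 / 62.4 | 7.4 |

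A 400,000-patient simulation of the same model agrees within simulation error.

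**Extending to k = 4.** With continuous detection the formula gives 3.6 to 4.3 points at 12 months and 7.2 to 10.2 at 24 months. Lesions are in fact seen at scans three months apart, and two lesions that arise between scans and lie within view are found together. With three-monthly detection, the same death hazard and shares of 40/50/10, k from 2 to 4 gives about 1.3 to 3.1 points at 12 months and 3.3 to 7.9 at 24 months.

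**Events lost.** Per 50 patients under the plan's accrual and follow-up, stopping at first progression keeps 14.9 events per endpoint (40/40/20) against 17.4, 19.3 and 20.7 with full collection at k = 1, 2 and 3. With 30/50/20 the local/regional count is about 11.2 against 13.6, 15.5 and 17.0. Roughly 2 to 6 events per endpoint are lost, some of them even where bias is nil.

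**Scale.** At N = 50 with no censoring, a 95% interval at 55% is ±1.96×√(0.55×0.45/50) = ±13.8 points; at 62% it is ±13.5.

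**The case against.** A reader might infer that patients are followed for survival only after progression, so that second-site lesions are never collected. The documents do not support that. Section 4.6 names overall survival but does not exclude anything else, and the clause that expressly ends disease-status follow-up covers only subjects who stopped for reasons other than progression. The opening sentence of 4.6, 5.3 and 5.4 keep visits and CT going, and treatment beyond progression is allowed. This is an unreconciled conflict, not a shown absence of data.

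Nor does 10.3.1 say that a patient is censored at first progression; it has no censoring rule at all. Informative censoring therefore needs two conditions: that 4.6 governs, and that failure at one site raises risk at the other. Neither is established by the documents.

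The size is also easily overstated. With shares of 40/50/10, no post-progression death and instant detection, the same model gives 6 to 14 points at 24 months for k from 2 to 4. Adding death and the scan interval roughly halves this. Both endpoints are secondary and descriptive, with no test or threshold, and the bias is smaller than the sampling error.

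All of this stands. Two things survive it. The only progression-specific sentence points away from collecting what the endpoint definitions require, and a general calendar does not clearly override it. And the analysis section lacks a rule under either reading. Sampling error does not excuse a bias of known direction that can be removed cheaply.

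**Conclusion.** The concern holds as a conflict within the plan. Section 4.6 names only overall survival as follow-up after documented progression. The rest of the follow-up plan schedules imaging without a stop, and both site endpoints count any lesion.

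If 4.6 governs, about 2 to 6 second-site events per endpoint would be lost in 50 patients. Freedom from distant and from local/regional failure would be overstated by about 1 to 3 points at 12 months and 3 to 8 at 24 months. These sizes rest on assumed site shares, a two- to fourfold hazard increase, a post-progression death hazard of 0.8 per year and three-monthly detection; none of the shares, multipliers or death hazard comes from the documents. The bias is nil if the sites are independent. If 5.4 governs, the events can be collected, but 4.6 still needs correcting and 10.3.1 still needs a censoring rule. The primary endpoint and N are unaffected, so this should be fixed but does not threaten the main result.

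**What to change.** Reconcile 4.6 with 5.3 and 5.4. Preferred: state in 4.6 that after first progression the date and site of the first distant and the first local/regional lesion continue to be recorded, from the 5.4 scans or available routine imaging, until both have occurred, death or withdrawal of consent. New anticancer therapy is recorded but does not end collection. Add to 10.3.1 how other-site progression, new therapy and death are handled for each endpoint.

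If post-progression sites of failure will not be collected, redefine both endpoints as site of first failure. In 10.3.1, replace Kaplan-Meier for these two by cumulative incidence, with failure at the other site and death as competing events.

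The cost is about one sentence in each section and two case report form fields; treatment does not change. The limits should be acknowledged. Post-progression imaging is less uniform, the scheduled CT covers only chest and adrenals so distant ascertainment stays incomplete, and later lesions partly reflect next-line therapy.
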